3.2. Study Treatment

Participants with ALS:

Cohort A: BIIB105 5 mg or placebo

Cohort B: BIIB105 20 mg or placebo

Cohort C1: BIIB105 60 mg or placebo

CONFIDENTIAL

The information contained herein may not be used, disclosed, or published without the written consent of Biogen MA Inc.

Cohort D1: BIIB105 120 mg or placebo

Participants with polyQ-ALS:

Cohort C2: BIIB105 60 mg or placebo

Cohort D2: BIIB105 120 mg or placebo

Participants in Cohorts A, B, C1, and C2 will receive 3 loading doses administered every 2 weeks (on Days 1, 15, and 29), followed by 2 maintenance doses administered once every 4 weeks (on Days 57 and 85), for a total of 5 doses over approximately 13 weeks.

Participants in Cohorts D1 and D2 will receive 3 loading doses administered every 2 weeks (on Days 1, 15, and 29), followed by 5 maintenance doses administered once every 4 weeks (on Days 57, 85, 113, 141, and 169), for a total of 8 doses over approximately 25 weeks.

3.3. Subgroup Variable

Subgroup analyses for selected endpoints may be performed by median baseline NfL level (median across FAS population).

Subgroup analyses for selected endpoints may also be performed based on genetic testing results (including, but not limited to, based on number of ATXN2 polyQ repeats, presence/absence of pathogenic/likely pathogenic mutations in SOD1, FUS, or TDP43 genes, by presence/absence of pathogenic expansions in the C9orf72 gene, or by number of risk alleles on the UNC13A gene).

3.4. Analysis Sets

1) FAS (Full Analysis Set) Population

The FAS population is defined as all randomized participants who received at least 1 dose of study treatment. In analyses performed on the FAS, participants will be analyzed, based on the intent-to-treat (ITT) principle, according to their randomized treatment assignment regardless of treatment received.

2) Safety Analysis Population

The safety analysis population is defined as all randomized participants who received at least 1 dose of study treatment. In the case of any participants who are mis-randomized, then any analyses based on the safety analysis population will be based on actual treatment received.

3) PK Analysis Population

CONFIDENTIAL

The information contained herein may not be used, disclosed, or published without the written consent of
Biogen MA Inc.

The PK analysis population is defined as all randomized participants who received at least 1 dose of study treatment and have at least 1 postdose serum and/or CSF BIIB105 measurement.

4) PD Population

The PD population is defined as participants who received at least 1 dose of study treatment and have at least 1 available postdose evaluation of the respective PD endpoint in the study.

[REDACTED]

[REDACTED]

[REDACTED]

4. List of Planned Study Analyses

4.1. Interim Analysis

There is no planned interim analysis for Part 1. However, as the data for Part 1 and Part 2 are in the same database, this is considered an interim lock.

Interim analysis of key safety, secondary, and [REDACTED] endpoints (including PK, PD, [REDACTED]) for Part 2 and integrated analyses based on unblinded data from Part 1 and interim data from Part 2 may be conducted; these will be discussed in a separate SAP.

The list of unblinding personnel and details of the unblinding procedure are provided in the 275AS101 Unblinding Plan. The study statistical programmers and biostatisticians will be unblinded following the interim lock. The BIIB105 275AS101 unblinded study team is listed in the Unblinding Plan. Participants, investigators and site staff and sponsor staff responsible for site monitoring and data management will remain blinded to Part 1 treatment assignments until Part 2 completes.

4.2. Primary Analysis

The primary analysis will be conducted after completion of Part 1 Day 175/176 visit for all cohorts (Cohorts A, B, C1, C2, D1, and D2).

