5.2. Study Duration for Participants

5.2.1. Study Duration for Participants in Part 1

The total Part 1 study duration for each participant in Cohorts A, B, C1, and C2 will be approximately 29 weeks:

- Screening Period of up to 4 weeks
- Treatment Period of 13 weeks
- Follow-up Period of approximately 12 weeks

Participants in Cohorts A, B, C1, and C2 will have up to 13 CVs and 9 TC during the study, which include at least 1 Screening Visit, 5 Dosing Visits of which the first dose will require an inpatient stay of 2 days, 7 Follow-up Visits, and 9 TC. All visits should be performed within the number of days from the nominal visit day, specified in Section 1. Visit days are calculated with respect to Day 1 (the date of first dose).

The total Part 1 study duration for each participant in D1 and D2 will be between approximately 29 and 41 weeks:

• Screening Period of up to 4 weeks

- Treatment Period of 25 weeks
- Follow-up Period of approximately 12 weeks (only completed if the participant does not enter Part 2 after the Treatment Period)

Participants in Cohorts D1 and D2 will have up to 19 CVs and 15 TCs which will include at least 1 Screening Visit, 8 Dosing Visits of which the first will require an inpatient stay of 2 days, up to 10 Follow-up Visits, and up to 15 TCs.

Participants in Cohorts D1 and D2 who enter Part 2 after their Treatment Period (after the Day 176 Visit) will not be required to complete the follow-up visits in Part 1 that occur after their enrollment in Part 2. Participants from Cohorts D1 and D2 who do not enter Part 2 will have two follow-up clinic visits and two TCs approximately 6 and 12 weeks after their last dosing visit.

Of note, if the Study Sponsor decides to terminate Part 1 without terminating Part 2, participants who are active in Part 1 at the time of the Sponsor's decision will have the opportunity to end Part 1 and screen and enroll into Part 2 prior to completing Week 25.

5.2.2. Study Duration for Participants in Part 2

Study duration for each participant in Part 2 will be up to approximately 172 weeks:

- Screening Period of up to 4 weeks (for participants from Cohorts D1 and D2, Screening Period begins with Day 169 Visit of Part 1)
- Treatment Period of up to approximately 156 weeks: either 104 weeks, OR until the last participant enrolled has had the opportunity for their Part 2 Day 365 visit (Week 52), whichever occurs later
- Follow-up Period of approximately 12 weeks

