5.6. End of Study

5.6.1. End of Part 1

The end of Part 1 (placebo-controlled study) is last participant, last visit in Part 1. Final analyses of Part 1 will be performed after the last participant, last visit has been completed for Part 1, and the database for Part 1 has been locked.

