275AS101 is a two part (Part 1 and Part 2) study. Part 1 is a Phase 1/2, randomized, double-blind, placebo-controlled, MAD evaluation of the safety, tolerability, PK, PD, and effect on clinical function of BIIB105.

Part 2 is an open-label extension study to assess the long-term safety, tolerability, pharmacokinetics, pharmacodynamics, and effects on disease progression of BIIB105 administered IT to adults with ALS and polyQ-ALS who complete Part 1 through Week 25.

The purpose of this Statistical Analysis Plan (SAP) is to describe the final statistical analyses of the Part 1 safety, tolerability, PK, PD, and effect on disease progression on BIIB105 up to Week 25 for cohort A (BIIB105 5 mg), cohort B (BIIB105 20 mg), cohort C1(BIIB105 60 mg), cohort C2 (BIIB105 60 mg for polyQ-ALS), cohort D1 (BIIB105 120 mg), and cohort D2 (BIIB105 120 mg for polyQ-ALS).

2. Study Overview

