The information contained herein may not be used, disclosed, or published without the written consent of
Biogen MA Inc.

[figure not shown]

Table 8 Analysis Visit Windows for CSF PK/PD data

Visit	Lower Bound (inclusive)	Upper Bound (inclusive)	Target Day	Cohort
Baseline ^(a)	Last record prior to dosing	Last record prior to dosing	1	All cohorts
Day 15 ^(a)	9	22	15	All cohorts
Day 29 ^(a)	23	43	29	All cohorts
Day 57 ^(a)	44	71	57	All cohorts

CONFIDENTIAL

The information contained herein may not be used, disclosed, or published without the written consent of
Biogen MA Inc.

Day 85 ^(a)	72	88	85	Cohorts A, B, C1, C2 only
Day 85 ^(a)	72	99	85	Cohorts D1, D2 only
Day 92	89	111	92	Cohorts A, B, C1, C2 only
Day 113	100	127	113	Cohorts D1, D2 only
Day 130	112	152	130	Cohorts A, B, C1, C2 only
Day 141	128	155	141	Cohorts D1, D2 only
Day 169	156	183	169	Cohorts D1, D2 participants who are dosed in Part 2 after Part 1 treatment period
Day 169	156	172	169	Cohorts D1, D2 participants who are not dosed in Part 2 after Part 1 treatment period
Day 175	153	189	175	Cohorts A, B, C1, C2 only
Day 176	173	195	176	Cohorts D1, D2 participants who are not dosed in Part 2 after Part 1 treatment period
Day 214	196	236	214	Cohorts D1, D2 participants who are not dosed in Part 2 after Part 1 treatment period
Day 259	237	273	259	Cohorts D1, D2 participants who are not dosed in Part 2 after Part 1 treatment period

CONFIDENTIAL

The information contained herein may not be used, disclosed, or published without the written consent of
 Biogen MA Inc.

Note: The lower bounds of visits are calculated as: target day - (target day – target day of previous visit)/2+1. The upper bounds of all visits are calculated as: target day + (target day of next visit – target day)/2 except for Day 175 for cohorts A, B, C1, and C2, which is calculated as: target day + 14, for Day 169 for cohorts D1, D2 participants who are dosed in Part 2 after Part 1 treatment period, and for Day 259 for cohorts D1, D2 participants who are not dosed in Part 2 after Part 1 treatment period, which is calculated as: target day + 14. Both lower and upper bounds are based on all cohort schedules.

(e) Common visits between Cohorts A, B, C1, C2, D1, and D2.

Table 9 Analysis Visit Windows for Plasma PD data

Visit	Lower Bound (inclusive)	Upper Bound (inclusive)	Target Day	Cohort
Baseline ^(a)	Last record prior to dosing	Last record prior to dosing	1	All cohorts
Day 29 ^(a)	16	43	29	All cohorts

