4.3. End of Long-term Follow-up Analysis

At the end of the open-label extension of the study (Part 2), to assess long-term safety and efficacy, analysis of safety, secondary, [REDACTED] endpoints (including PK, PD, clinical function) for Part 2 and integrated analysis of Part 1 and Part 2 will be conducted.

This SAP will only cover the primary analysis for Part 1 once Part 1 Day 175/176 visit has been completed for all cohorts. A separate SAP will detail the integrated analysis.

5. Statistical Methods for Planned Analyses

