3.4. Analysis Sets

Part 1

1) Part 1 FAS Population

The Part 1 FAS population is defined as all randomized participants who received at least 1 dose of study treatment in Part 1. In analyses performed on the FAS, participants will be analyzed, based on the intent-to-treat (ITT) principle, according to their randomized treatment assignment regardless of treatment received.

2) Part 1 Safety Analysis Population

The Part 1 safety analysis population is defined as all randomized participants who received at least 1 dose of study treatment in Part 1. In the case of any subjects who are mis-randomized, then any analyses based on the safety analysis population will be based on actual treatment received.

3) Part 1 PK Analysis Population

The Part 1 PK analysis population is defined as all randomized participants who received at least 1 dose of study treatment and have at least 1 postdose serum and/or CSF BIIB105 measurement in Part 1.

4) Part 1 PD Population

The Part 1 PD population is defined as subjects who received at least 1 dose of study treatment and have at least 1 available postdose evaluation of the respective PD endpoint in the study in Part 1.

5) Part 1 Clinical Function Population

The Part 1 clinical function population is defined as the subset of the FAS population who have at least 1 postdose measurement in Part 1.

Part 2

1) Part 2 FAS Population

The Part 2 FAS population is defined as all enrolled participants who received at least 1 dose of study treatment in Part 2.

2) Part 2 Safety Analysis Population

The Part 2 safety analysis population is defined as all participants who received at least 1 dose of study treatment in Part 2.

Integrated Part 1 and Part 2

Integrated data for Part 1 and Part 2 will be analyzed based on the following populations defined for Part 1, with the exception of the safety data, which will be defined separately:

CONFIDENTIAL

The information contained herein may not be used, disclosed, or published without the written consent of
Biogen MA Inc.

Part 1 FAS population, Part 1 PK population, Part 1 PD population, and Part 1 clinical function population.

The Integrated Part 1 and Part 2 safety analysis population is defined as all randomized participants who received at least 1 dose of BIIB105 either in Part 1 or Part 2.

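### The final and only Part 1 safety analysis is triggered at Day 175/176, before the last Part 1 visit that the protocol requires, and late adverse events of placebo participants who do not enter Part 2 reach no later safety summary

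*SAP*

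**What the plan says.** **Protocol.** Section 5.6.1 defines the end of Part 1 as the last participant's last Part 1 visit and adds: "Final analyses of Part 1 will be performed after the last participant, last visit has been completed for Part 1". Section 5.2.1 sets the remaining schedule: "Participants from Cohorts D1 and D2 who do not enter Part 2 will have two follow-up clinic visits and two TCs". Table 2 puts those clinic visits at Days 214 and 259 and the calls at Days 215 and 260. Section 12.3.1 has AEs recorded from first dose to the Final/ET Visit. The Part 1 primary endpoint (section 4) is the incidence of AEs and SAEs in Part 1.

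**Part 1 SAP.** The Introduction says its purpose is to "describe the final statistical analyses of the Part 1 safety, tolerability, PK, PD" and disease-progression effects up to Week 25. Section 4.1 says "There is no planned interim analysis for Part 1", but calls the lock an interim lock because both parts share one database. Section 4.2 gives the trigger: "The primary analysis will be conducted after completion of Part 1 Day 175/176 visit for all cohorts". Section 4.3 closes the scope: "This SAP will only cover the primary analysis for Part 1 once Part 1 Day 175/176 visit has been completed for all cohorts". Tables 8 and 9 in section 3.1 nevertheless define Day 214 and Day 259 windows for "Cohorts D1, D2 participants who are not dosed in Part 2 after Part 1 treatment period". The one change visible in section 6 concerns time-to-event analyses from symptom onset.

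**Part 2/integrated SAP.** Section 3.4 defines the integrated safety population as "all randomized participants who received at least 1 dose of BIIB105 either in Part 1 or Part 2". The Part 2 safety population requires a dose in Part 2.

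**The concern.** The protocol ties the final Part 1 analysis to the last Part 1 visit. The Part 1 SAP ties it to an earlier visit, calls it final, and plans nothing afterwards. For Cohorts A, B, C1 and C2 this hardly matters, because Day 175 is their final clinic visit. For D1/D2 participants who do not enter Part 2, up to two scheduled safety visits can fall after the trigger.

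The primary endpoint is at stake. Whether a non-rollover's last weeks are counted depends on how early that person enrolled. The later document does not restore the balance: its AE tables can pick up late events on BIIB105 but not on placebo. The only AE summary with a placebo arm is the Part 1 one, and it is never updated.

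**Working it through.** **Planned counts** (protocol 5.3.1)
- Total: 8 + 8 + 12 + 4 + 48 + 18 = 98, which reproduces the stated total.
- Placebo in A, B, C1 and D1: 2 + 2 + 3 + 12 = 19, which reproduces the pooled placebo N in protocol 13.5.
- All placebo: 19 + 1 + 6 = 26. Placebo in D1/D2: 12 + 6 = 18.

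**Length of the gap** (protocol Table 2)
- After the Day 169 dose: 214 − 169 = 45 days (6.4 weeks) and 259 − 169 = 90 days (12.9 weeks), in line with the stated approximate 6 and 12 weeks.
- After Day 176: 214 − 176 = 38 days and 259 − 176 = 83 days (11.9 weeks).
- Share of the schedule: 83/259 = 32%.

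**Who is cut short.** Let d be the number of days by which a non-rollover's Day 176 precedes the last participant's Day 176. At the trigger that person has been followed to Day 176 + d.
- If d ≥ 83, nothing is lost.
- If d < 83, then 83 − d days are unobserved.
- If d < 38, the Day 214 visit is also missed.

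These figures ignore visit windows and any data that accrue between trigger and lock.

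**Where a late event goes in the Part 2/integrated SAP**
- *AE or non-fatal SAE, BIIB105 non-rollover:* in the 120 mg pools. Table 4 includes D1/D2 participants exposed in Part 1 whether or not they entered Part 2.
- *AE or non-fatal SAE, placebo non-rollover:* in neither safety population (section 3.4), and Table 5 has no placebo column. At most it appears in a listing (sections 5.1 and 5.7.1).
- *Death, permanent ventilation, or withdrawal for progression, placebo non-rollover:* analysed. Section 3.5 keeps D1/D2 placebo participants in the delayed-start group whether or not they roll over. Section 5.6.5 compares time to event by group, and section 5.2 tabulates Part 1 deaths and withdrawals.
- *Day 214/259 function data, placebo non-rollover:* mapped to analysis visits (section 3.1) and analysed.

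**How many people.** The documents give no non-rollover rate. Assume 10% to 30% of the 18 D1/D2 placebo participants: 1.8 to 5.4, or about 2 to 5 people. This is an upper bound, because it counts non-rollovers with d ≥ 83 and those who died or withdrew before follow-up. Assume further a 10% to 50% chance of an event in the follow-up period. The expected number of placebo participants with an unsummarised event is then at most 1.8 × 0.10 = 0.18 to 5.4 × 0.50 = 2.70.

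**The case against.** Several stronger readings are tempting. The documents do not support them.

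- *Late placebo events vanish from every later analysis.* They do not. Deaths, permanent ventilation, withdrawal for progression and function data are analysed, and AEs may be listed. The gap is confined to summaries of AEs and non-fatal SAEs.
- *An analysis at Day 175/176 is not allowed.* Protocol 13.4 permits unblinded Part 1 analyses once a cohort has completed dosing, and the last D1/D2 dose is on Day 169. The defect is that this look serves as the final and only Part 1 analysis.
- *The SAP discards all data after Day 176.* The Week 25 wording could be read so, but section 4.2 says when the analysis runs and sets no data cut-off. The Day 214 and Day 259 windows fit the use of whatever has accrued by the lock.
- *The randomised comparison loses a third of its follow-up.* After Day 176, rollovers leave Part 1 follow-up and placebo rollovers start BIIB105. What remains is self-selected, so a Day 176–259 comparison is not protected by randomisation. The calendar cut applies to both arms, and section 5.7.1 of the Part 1 SAP plans exposure- and follow-up-adjusted rates.
- *Non-rollovers are mainly people with toxicity or fast progression.* The documents say nothing on this.

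It is also fair to say that the BIIB105-only integrated safety set follows protocol 13.2.3 and 13.3.1, and that placebo-period data of rollovers are left out of the 120 mg pool too. The Part 1 SAP did not create that rule. But because of it, a missed placebo event cannot be recovered later.

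What remains is the undeclared departure from protocol 5.6.1 and the absence of any later placebo AE summary. Adjusted rates correct the denominators; they do not supply events that had not been observed at the cut.

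**Conclusion.** The concern holds in a narrow form. The Part 1 SAP makes an analysis at Day 175/176 the final one, against protocol 5.6.1, without declaring it in the visible text of section 6. Followed as written, AEs and non-fatal SAEs after the cut in D1/D2 placebo non-rollovers reach no planned safety summary, while those of BIIB105 non-rollovers reach the 120 mg pools.

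The loss is up to 83 days per affected person, and only for those with d < 83. The number is not stated and is probably small: about 2 to 5 placebo participants at most under the assumed 10% to 30% non-rollover share. The integrated SAP's disposition table has a category for participants still in Part 1 at the interim (section 5.2), so the case was foreseen. The conclusion assumes that no undisclosed passage of section 6 declares the timing. It does not imply that the Part 1 safety results are biased in a known direction.

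**What to change.** 1. Keep the Day 175/176 analysis if it is wanted, but declare its timing in section 6 of the Part 1 SAP as a change from protocol 5.6.1, and amend sections 4.2 and 4.3 so that it is not the last Part 1 safety analysis.
2. Rerun the Part 1 AE/SAE tables, including the exposure- and follow-up-adjusted rates, by treatment arm once at the final lock with all Part 1 follow-up. Include placebo non-rollovers. Add these tables to the safety section (5.7) of the integrated SAP.
3. State in both documents that the Day 176–259 data come from self-selected non-rollovers and are descriptive.

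The cost is SAP wording and one rerun of existing tables, with no new data collection. No delay follows either. Section 4.1 of the integrated SAP has all Day 175/176 visits complete before the 29 April 2024 lock. Adding 83 days puts any outstanding Day 259 visit at about 21 July 2024 at the latest, before visit windows, and that SAP is dated 5 September 2024.

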4.3. End of Long-term Follow-up Analysis

At the end of the open-label extension of the study (Part 2), to assess long-term safety and efficacy, analysis of safety, secondary, [REDACTED] endpoints (including PK, PD, clinical function) for Part 2 and integrated analysis of Part 1 and Part 2 will be conducted.

This SAP will only cover the primary analysis for Part 1 once Part 1 Day 175/176 visit has been completed for all cohorts. A separate SAP will detail the integrated analysis.

5. Statistical Methods for Planned Analyses

5.1. General Principles

Descriptive summary statistics will be presented for all primary, secondary, [REDACTED] endpoints collected. Unless otherwise specified, for continuous endpoints, the summary

CONFIDENTIAL

The information contained herein may not be used, disclosed, or published without the written consent of Biogen MA Inc.

statistics will generally include number of participants with data, mean, standard deviation, median, first and third quantiles and range. For categorical endpoints, the summary statistics will generally include number of participants with data, frequency counts and the percentage of those with data in each category.

Analyses will be performed on the data from Part 1 alone.

Placebo data may be pooled across cohorts for analyses. The “Pooled Placebo 1” population is defined as participants from Cohort A, B, C1, and D1 who received placebo. The “Pooled Placebo 2” population is defined as participants from Cohort C2 and D2 who received placebo.

As a general rule, any visit/dose group combination that only has data for 1 participant will not be presented in group plots. All data will be listed, unless otherwise specified.

The statistical software, SAS® Version 9.4 or above, will be used for all summaries and statistical analyses.

5.2. Participant Accountability

The summaries will be presented by dose level and treatment assignment (BIIB105 5 mg [Cohort A], 20 mg [Cohort B], 60 mg [Cohorts C1+ C2], 120 mg [Cohorts D1+D2], Pooled Placebo 1+Pooled Placebo 2). Selected summaries will also be presented by cohort and treatment assignment in Part 1 (BIIB105-treated Cohorts A, B, C1, C2, D1, and D2; Pooled Placebo 1 and Pooled Placebo 2), and for all participants.

The number (and percentage) of participants randomized; dosed; completed the treatment; completed Part 1; completed Part 1 treatment period but missed one or more doses; discontinued treatment and the reasons for discontinuation; and withdrew from Part 1 early and the reasons for withdrawal will be summarized in a table. The number of participants who enrolled and completed Part 1 will be summarized. The number of participants who completed up to Part 1 Day 175/176 visit will be summarized. The number (and percentage) of participants who enrolled in Part 2 will also be summarized.

A listing of participants who discontinued treatment/withdrew from Part 1 and the associated reasons for discontinuation/withdrawal will be presented.

The number (and percentage) of participants by analysis population will be summarized.

